allergies/hypersensitivities exist to Panax species, their constituents, or to other members of the Araliaceae family. Cardiovascular: Arterial hypertension has been reported. However, one double-blind study failed to find any effect on blood pressure [110]. In 1979, an article was published in the Journal of the American Medical Association that claimed that people can become addicted to P. ginseng and experience blood pressure elevations, nervousness, sleeplessness, diarrhea, and hypersexuality, this condition was termed as ginseng abuse syndrome [111]. However, this report has since been thoroughly discredited and should no longer be taken seriously[112,113]. One case report and one double-blind trial suggest that P. ginseng can reduce the anticoagulant effects of Coumadin (warfarin) [114,115], but another trial did not find such an interaction [111]. The reason for this discrepancy is not clear. Psychiatric: Concomitant use of *P. ginseng* and the monoamine oxidase inhibitor phenelzine (Nardil) may result in manic-like symptoms [39,116]. Hepatotoxic effects: Ginseng may increase the toxicity of hepatotoxic agents. Ginseng has been well tolerated in prior studies(Barton etal 2009). However possible interactions with hepatoxic agents (Miller LG Herbal medicinals: selected clinical considerations focusing on known or potential drug-herb interactions. Arch Intern Med 1998 Nov 9;158(20):2200) such as coumadin with reported increase in bleeding time. Hence we would monitor the PT/INR weekly for patients on coumadin and liver function test every 2 weeks (Total bilirubin </=1.5 mg/dL, and AST (SGOT) and ALT (SGPT) </=2 x ULN or </= 5 x ULN)if hepatic metastases are present or if patients are on potentially hepatoxic agents such as acetaminophen or statins. Patients with a history of hepatitis A, B and C will be excluded. Endocrine: There has been a few case reports of breast tenderness, postmenopausal vaginal bleeding, and menstrual abnormalities associated with Panax ginseng use [109,116]. Such side effects suggest that it has estrogenic properties. However, a large double-blind trial of P. ginseng found no estrogen-like effects [83] and a carefully designed in vitro study no estrogenic activity [120,121]. Ginseng decreased fasting blood glucose in both diabetic and non-diabetic patients and therefore combination use may lead to additive effects. Pregnancy and teratogeneity: Chinese tradition suggests that P. ginseng should not be used by pregnant or nursing mothers, and one animal study showed that ginseng use by a pregnant mother could cause birth defects [119-121]. In the proposed study, we plan to exclude patients with a psychiatric diagnosis, uncontrolled hypertension or arrhythmia, and diabetes; pregnant or lactating women; and patients taking anticoagulants, MAOIs [39,109], and tricyclic drugs. We will carefully monitor patients for adverse events and interactions with various medications, as described in Table 3.

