CBC, Electrolytes, Total bilirubin, and AST (SGOT) and ALT (SGPT will be done at Baseline, CBC and Electrolytes will be done at Day 15+/- 3days and Day 29+/- 3days. We would monitor the PT/INR weekly for patients on coumadin and liver function test every 2 weeks (Total bilirubin, and AST (SGOT) and ALT (SGPT) if hepatic metastases are present or if patients are on potentially hepatoxic agents such as acetaminophen or statins. Laboratory studies will be performed at baseline, day 15, and day 29. Hematology and chemistry blood collection will be performed on the expanded open label cohort of patients at Day 57 or conclusion of P. ginseng. Patient can have the labs drawn at outside facility. The research nurse will obtain results from outside labs via fax, or email. Patients entered on the open label phase will be followed until their respective study conclusion.

Day 15, 29, and 57 safety labs and Day 15 and 29 optional research blood will be collected only if patient returns to MDACC for the follow-up visits.

Dose Continuation, Modification and Interruption

II. Dose Continuation, Modification and Interruption

Subjects will be evaluated for AEs with the NCI CTCAE v4.0 as a guide for the grading of severity.

Table A outlines Panax ginseng/placebo dose reduction steps

Table A: Panax ginseng/ placebo Dose Reduction Steps				
Starting Dose	400mg capsule or identical placebo orally BID for 28 days			
Dose Level –1	400 mg daily or identical placebo for rest of the treatment phase (up to day 29)			

INSTRUCTION FOR INITIATION OF A WEEK 3, AND OPEN LABEL

Prior to initiation of treatment of day 15, and open label phase (Day 29) the patient should have:

We would monitor the PT/INR weekly for patients on coumadin and liver function test every 2 weeks[day 15 +/-3 days, and day 29+/-3 days (Total bilirubin </=1.5 mg/dL, and AST (SGOT) and ALT (SGPT) </=2 x ULN or </= 5 x ULN)if hepatic metastases are present or if patients are on potentially hepatoxic agents such as acetaminophen or statins.

- Any Panax ginseng-related or identical placebo related allergic reaction/hypersensitivity that may have occurred has resolved to ≤ grade 1 severity;
- Any other Panax ginseng-related or identical placebo -related adverse event that may have occurred has resolved to ≤ grade 2 severity.

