If these conditions are not met on Day 15 or Day 29 (all +/- 3 days), the subject will be evaluated weekly and Panax ginseng will not be initiated until the toxicity has resolved as described above. The patient can be off the drug for a total 1 week before being removed from the treatment phase of the study.

January 21, 2016 Page 15 of 33 INSTRUCTIONS FOR DOSE MODIFICATIONS OR INTERRUPTION DURING A TREATMENT PHASE.

NCI CTC 4 Toxicity Grade	Day 2- 57
Grade≥ 2 neutropenia related to Panax ginseng or placebo associated with fever (temperature ≥ 38.5° C) or Grade 4 neutropenia	 Discontinue Panax ginseng study drug or identical placebo.
Thrombocytopenia Panax ginseng or placebo ≥Grade 2 (platelet count < 50,000/mm³)	 Discontinue Panax ginseng study drug or identical placebo
Steven Johnson syndrome	 Discontinue Panax ginseng study drug or identical placebo
Desquamating (blistering) rash- any Grade	 Discontinue Panax ginseng study drug or identical placebo.
Rash, Erythema multiforme ≥ ≥Grade 2	 Discontinue Panax ginseng study drug or identical placebo.
Hypertension, Hypotension, cardiac arrhythmia ≥Grade 2	 Hold (interrupt) dose, Up to one week before taking off study Follow at least weekly. If the toxicity resolves to ≤ grade 1 restart dose at (400mg) level and continue the study medication with continued monitoring as prescribed in the protocol. If the patient has repeat cardiac arrhythmias ≥ Grade 2. He will be discontinued from the study medication and monitored.
≥ Grade 3	Discontinue Panax ginseng study drug or identical placebo.
Allergic reaction or hypersensitivity ≥Grade 2	 Hold (interrupt) dose, Up to one week before taking off study Follow at least weekly. If the toxicity resolves to ≤ grade 1 restart dose at (400mg) level and continue the study medication with continued monitoring as prescribed in the protocol. If the patient has repeat ≥ Grade 2 allergic or hypersensitivity reaction, he will be discontinued from the study medication and monitored.
>/= Grade 4	 Discontinue Panax ginseng study drug or identical placebo
	placebo.

NCI CTC 4 Toxicity Grade	Day 2- 57

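### The laboratory schedule allows outside blood draws, then limits the Day 15, 29 and 57 safety labs to patients who return to the centre

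*Combined protocol and SAP*

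**What the plan says.** All the text is in the combined protocol and SAP.

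- **Schedule (C.6.2, laboratory paragraph).** "Laboratory studies will be performed at baseline, day 15, and day 29". Blood count and electrolytes are due at Days 15 and 29 for everyone. Liver tests are due every two weeks for patients with liver metastases or on drugs such as acetaminophen or statins. The open-label cohort has haematology and chemistry at Day 57 or when ginseng ends.
- **Outside draws (same paragraph).** "Patient can have the labs drawn at outside facility". "The research nurse will obtain results from outside labs via fax, or email".
- **Restriction (next paragraph).** "Day 15, 29, and 57 safety labs and Day 15 and 29 optional research blood will be collected only if patient returns to MDACC".
- **Condition for dosing (instruction for week 3 and open label).** The liver tests, with numerical limits, come under the lead-in "Prior to initiation of treatment of day 15, and open label phase (Day 29) the patient should have". If the conditions fail, the patient is evaluated weekly and "Panax ginseng will not be initiated until the toxicity has resolved as described above". A patient may be off drug for one week in total before leaving the treatment phase.
- **Major violation (III. Discontinuation of Study Treatment).** Absent safety laboratory tests are named as a major violation, as determined by the PI. A major violation is a reason to stop study drug.
- **Telephone follow-up (notes to Table 3).** A patient who cannot attend on Day 15, 29, 36 or 57 completes the questionnaires by telephone. The note does not mention laboratory tests.

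**The concern.** An outside draw is, by its nature, made without returning to the centre. One sentence permits it and a later one excludes it for the same tests. The plan expects some patients not to return, so staff will meet this case. The text would support three different actions for the same patient: use an outside laboratory, carry on without labs, or report a violation.

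The stake is safety monitoring. Section B.7 gives the reason for the liver tests: "Ginseng may increase the toxicity of hepatotoxic agents". The toxicity calls would pick up symptoms but not a silent rise in liver enzymes. The blood count matters too, because the dose-modification table has stopping rules for neutropenia and thrombocytopenia, and patients on chemotherapy may enrol.

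**Working it through.** The plan has no figure of its own to reproduce here. The check compares the rules and then does one short piece of date arithmetic.

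**Can the two laboratory sentences be reconciled?**

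1. Suppose the outside-draw permission covers all post-baseline labs. It then conflicts with the restriction at Days 15, 29 and 57.
2. Suppose it covers only the open-label Day 57 labs, because it follows that sentence. The restriction also names Day 57, so the conflict remains there, and Days 15 and 29 have no off-site route at all.
3. Suppose the restriction concerns only blood taken by the centre's own staff. The text does not say so, and its condition carries no exception for outside results.

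No reading stated in the text removes the conflict.

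**What is lost if the restriction is followed literally?** For a patient followed by telephone at Day 15:

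- blood count and electrolytes: due for all patients, not collected;
- bilirubin, AST and ALT: due for at-risk patients, not collected;
- questionnaires, including FACIT-F: still collected by telephone.

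**How does that sit with the other rules?**

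- The week 3 instruction makes the liver tests a condition for Day 15 and open-label dosing. The restriction stops the condition from being checked.
- The hold is triggered when the conditions are not met, and a missing result can fairly be read as that. The release, however, is that toxicity has resolved. With no result there may be no toxicity to resolve, so the text does not say when drug restarts.
- Section III lists as a major violation an omission that C.6.2 permits.

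**Delay for an at-risk patient if Day 15 is skipped and drug continues.** Inputs: visits at Days 15 and 29, each with a window of 3 days either side; first dose on Day 1 (assumption).

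- Formula: days from first dose to first on-treatment liver test = test day − 1.
- As planned: 15 − 1 = 14 (window 11 to 17).
- Day 15 skipped: 29 − 1 = 28 (window 25 to 31).
- Ratio: 28 / 14 = 2.
- On-treatment liver tests through Day 29 fall from 2 to 1.

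**The case against.** The strongest reply is that the plan already blocks the harmful outcome. The liver tests are a condition for further dosing, the hold applies whenever conditions are not met, and missing safety labs are a major violation that can stop drug. Toxicity is also reviewed on Days 8, 15, 21, 29, 36, 43 and 57, and patients with a history of hepatitis A, B or C are excluded. Much of this stands. These rules are real safeguards, though partial: the release wording does not fit a missing result, and the violation rule acts after the omission and at the PI's determination.

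A second reply is that the outside-draw sentence may be meant for other tests, such as the weekly PT/INR for coumadin patients, some of which falls on days marked for telephone or in-person contact. That is plausible, but the text does not say it, and the sentence stands beside the general laboratory schedule.

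A reader might go further and infer that the plan lets at-risk patients pass through the double-blind phase and into open label with no liver test. The documents do not support that. It would need the Day 15 and Day 29 conditions both to be ignored and the violation rule not to be applied.

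**Conclusion.** The contradiction in C.6.2 is real and no stated reading resolves it. Followed literally, the restriction drops on-treatment safety labs for patients followed by telephone, and it is out of step with the dosing condition and the major-violation rule.

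The size is limited. In an at-risk patient whose Day 15 tests are skipped while drug continues, the first on-treatment liver test comes at about 28 days instead of about 14. This rests on a first dose on Day 1 and on the hold not being applied. The documents give neither the share of telephone visits nor the share of at-risk patients, so no count for the trial can be offered.

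The point concerns safety monitoring and operations. It does not bear on sample size, power or type I error.

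**What to change.** 1. In C.6.2, apply the return-to-centre condition to the optional research blood only. State that the Day 15, 29 and 57 safety labs are to be drawn either at the centre or at an outside facility. The route for obtaining outside results is already written.
2. In the instruction for week 3 and open label, state that a missing required liver result counts as a condition not met, and that drug is held, within the existing one-week limit, until the result is available.
3. Leave the major-violation rule in section III unchanged.

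No new tests or centre visits are needed. The cost is an outside blood draw for patients who cannot travel and, for an at-risk patient whose result is late, a possible short hold. The existing window already allows the Day 15 draw from Day 12 (15 − 3), so most holds should be avoidable.

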- 2. Rate fatigue on a numerical scale during the previous 24 hours as \geq 4 on a 0 to 10 scale (0 = no fatigue and 10 = worst possible fatigue).
- 3. Describe fatigue as being present every day for most of the day for a minimum of 2 weeks.
- 4. Memorial delirum assessment scale </= 13.
- 5. Are 18 years or older.
- 6. Hemoglobin level of ≥8 g/dL within 2 weeks of enrollment. If the patient has not had blood drawn for a hemoglobin level in the previous two weeks, one will be performed to determine eligibility. Patients with a hemoglobin level <9g/dL will be evaluated for treatment of anemia.

- 7. Able to understand and sign the informed consent.
- 8. No concurrent use of chronic systemic steroids (defined as currently on more than 1 week of treatment).
- 9. Controlled pain and depression symptoms, if present (defined as no change in the Morphine equivalent dose of 30% or change in the dose of antidepressant medication in the past 2 weeks)
- 10. Patients should have a Zubrod </= 2.
- 11. All patients who are receiving chemotherapy and/or radiation therapy are eligible for study if they have completed at least one cycle of chemotherapy or targeted therapy, or > 1 week of radiation therapy, and if they have been approved to go on study by their primary oncologist. The PI/designated research staff of this study will obtain and document approval from the primary oncologist and principal investigator of the clinical trial in case the patient is on another clinical trial as referenced in the patient's study documents.
- 12. Negative pregnancy test for women of childbearing potential, as defined by intact uterus and ovaries, and a history of menses within the last 12 months. Pregnancy test to be performed no greater than 14 days prior to consent in study. In cases of women with elevated b-HCG, these candidates will be eligible to participate so long as the level of b-HCG is not consistent with

pregnancy. Women of childbearing potential need to be on or use contraception, or be abstinent during the study period. Their male partners must also use contraception (condom) or maintain abstinence.

Birth controls specifications: Women who are able to become pregnant must use birth control during the study and for 30 days after the last ginseng/placebo dose.

Acceptable forms of birth control include barrier methods (such as condom or diaphragm) with spermicide.

C.3.2.2. Exclusion Criteria

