- 1. Major contraindication to ginseng: allergy/hypersensitivity to *Panax* species or their constituents (history of arrhythmias, agitation, or motor tics, or severe angina pectoris).
- 2. Currently taking ginseng, methylphenidate or modafinil or have taken it within the previous 10 days.
- 3. Inability to complete the baseline assessment forms or to understand the recommendations for participation in the study.
- 4. Currently with a diagnosis of major depression, manic depressive disorder, obsessive-compulsive disorder, or schizophrenia).
- 5. Symptomatic tachycardia and uncontrolled hypertension (determined to be clinically significant by the PI).
- 6. Currently receiving phenobarbital, diphenylhydantione, primidone, phenylbutazone, MAOIs, clonidine and tricyclic antidepressant drugs
- 7. Uncontrolled diabetes mellitus as defined by a random blood sugar of >200mg/dl not being monitored by their primary care physician.
- 8. No concurrent full dose anticoagulant therapy. </= 1 mg/day of coumadin for preventing catheter clots allowed.
- 9. History of hepatitis A, B and C.
- 10. Women who are nursing.

C.4. Rationale for Different Tumor types:

On the basis of clinical trials of methylphenidate [127,128,130,139], donepezil [129,130] and fish oil [132], in the treatment of cancer related fatigue by our group and studies by other groups [140-144] the frequency, severity and mechanisms of fatigue in cancer patients with different tumor types are largely the same. By including patients having fatigue with different tumor types, we will obtain a more representative distribution of patients in terms of age, sex and behavioral than we would in a study of patients with a single tumor type. Despite the different tumor type the expression of fatigue is a result of common pathophysiology (such as dysregulation of cytokines such IL-1 β , IL-6, IL-10 and TNF- α) in patients with cancer. As there are no cancer type-specific studies using ginseng for cancer related fatigue, we would use the preliminary data obtained from the responses to individual cancer types in this study. Future cancer specific studies will be designed based on these results. In addition, we have added collaborators from other departments and clinics who are currently treating patients with these diseases.

C.5. Randomization

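### Liver-function limits appear among the Day-15 and Day-29 dosing conditions, but entry has no matching limit and no rule uses the baseline liver tests

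*Combined protocol and SAP*

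**What the plan says.** - **Liver concern (B.7 Adverse Reactions).** The plan warns: "Hepatotoxic effects: Ginseng may increase the toxicity of hepatotoxic agents". Its response is liver testing every two weeks in some patients, with numeric limits in parentheses.
- **Entry (C.3.2.1 and C.3.2.2).** There are 12 inclusion and 10 exclusion criteria. Hemoglobin and random blood sugar have numeric limits; bilirubin, AST and ALT have none. The only liver-related criterion is "History of hepatitis A, B and C".
- **Baseline tests (C.6.2 and the Table 3 footnote).** "CBC, Electrolytes, Total bilirubin, and AST (SGOT) and ALT (SGPT will be done at Baseline". No rule acts on the result.
- **Dosing conditions (Dose Continuation, Modification and Interruption; instruction for week 3 and open label).** The list opens with "Prior to initiation of treatment of day 15, and open label phase (Day 29) the patient should have". The first item under it is a sentence about monitoring that contains "Total bilirubin </=1.5 mg/dL, and AST (SGOT) and ALT (SGPT) </=2 x ULN or </= 5 x ULN)if hepatic metastases are present". Two bullets follow, on allergic reactions and on other adverse events. Both are confined to events related to ginseng or placebo, which must have resolved to a stated grade.
- **Who is tested.** Two-weekly liver tests apply "if hepatic metastases are present or if patients are on potentially hepatoxic agents such as acetaminophen or statins". Routine Day-15 laboratory work is blood count and electrolytes only.
- **Consequence (same section).** If the conditions are not met on Day 15 or Day 29, the patient is evaluated weekly and drug is withheld until the toxicity has resolved. "The patient can be off the drug for a total 1 week before being removed from the treatment phase of the study".

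**The concern.** The plan appears to apply a liver standard at Day 15 that it does not apply on Day 1, although the tests that would settle the matter are drawn at baseline. A patient already above the limits can meet every entry criterion, take study drug for two weeks, and then fail a condition that the patient would have failed before the first dose. The text calls what must resolve a toxicity, yet here the abnormality predates the drug.

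Two things are at stake. The first is exposure of patients whom the plan, on this reading, would not continue to dose. The second is treatment cut short before the Day-29 FACIT-F assessment for a reason that was knowable at entry.

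**Working it through.** **1. Entry set beside the dosing condition.** Take a hypothetical patient with liver metastases, bilirubin 3 mg/dL and AST 8 x ULN at baseline, who otherwise meets every criterion.

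| Point | Rule in the plan | Result |
|---|---|---|
| Entry | No bilirubin, AST or ALT limit | Eligible |
| Baseline | Liver tests drawn, no rule attached | Dosing starts |
| Day 15 | Bilirubin up to 1.5 mg/dL; AST/ALT up to 2 x or 5 x ULN | Fails, values unchanged |
| After Day 15 | At most 1 week off drug | Removed from treatment phase |

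The AST value exceeds both multiples, so the result does not depend on which one the closing *if* clause governs. The two neighbouring bullets require relatedness to study drug. The liver limits require neither relatedness nor a change from baseline.

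**2. Timing.** Visits have a window of +/- 3 days, and the hold is limited to 7 days.
- Hold from Day 15: 15 + 7 = Day 22.
- Earliest hold, Day 12: 12 + 7 = Day 19.
- Latest hold, Day 18: 18 + 7 = Day 25.
- Earliest Day-29 visit: 29 - 3 = Day 26.

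The one-week limit is therefore reached before the primary assessment in every case. With dosing from Day 1, the patient has taken 11 to 17 days of the 29 in C.6.1 (11/29 = 38% to 17/29 = 59%; 14/29 = 48% for a hold from Day 15).

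**3. The plan's own sample size (Power Considerations).** Inputs: difference 3.3, SD 5.8, two-sided 0.05, 80% power, 50 evaluable and 64 recruited per group, 20% dropout.
- n per group = 2 x (1.960 + 0.842)^2 x 5.8^2 / 3.3^2 = 48.5, so 49 against the stated 50.
- Power with 50: 3.3 / (5.8 x sqrt(2/50)) = 2.845, and 2.845 - 1.960 = 0.885, giving 81.2%.
- Recruitment: 50 / 0.80 = 62.5, so 63 against the stated 64.

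The plan's figures reproduce. Loss can reach 1 - 50/64 = 21.9% before a group falls below 50, so there is little room beyond the planned 20%.

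**4. What loss would cost, if it occurred.** The documents give no rate of raised baseline liver tests. Let q be the share of *all* randomised patients who are in the tested subgroup, above the limits at baseline, held and removed, and also missing from the primary analysis. Assume q comes on top of the full 20% dropout. Evaluable n per group = 64 x (0.80 - q).

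| q (assumed) | Evaluable per group | Power at 3.3 points |
|---|---|---|
| 0% | 51.2 | 82.1% |
| 2% | 49.9 | 81.1% |
| 5% | 48.0 | 79.6% |
| 10% | 44.8 | 76.8% |

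This shows sensitivity only; it does not estimate q.

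**The case against.** **The limits may be monitoring thresholds.** The governing verb of the sentence is to monitor. B.7 uses almost the same sentence, with the same limits, purely as monitoring. The versions in C.6.2 and the Table 3 footnote carry no limits. The withholding rule waits for a toxicity to resolve, and only the two bullets on drug-related events speak of resolution. On that reading a stable, pre-existing abnormality triggers no hold. This objection stands as far as showing real ambiguity. It does not dispose of the point: the sentence sits under a heading about what the patient should have before treatment, and the next paragraph refers to these conditions. If only monitoring was meant, the numbers have no function and the text still needs correction.

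**A reader might infer that any randomised patient could be caught.** The documents do not support this. Two-weekly liver tests cover only the subgroup, and one sentence in C.6.2 limits Day-15 safety laboratory work to patients who return to the centre, although outside laboratories are allowed elsewhere in that section.

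**A reader might infer that these patients are lost from the primary analysis.** That is not established. Removal is from the treatment phase. The text after Table 3 allows FACIT-F to be taken by telephone on Day 29. C.9 aims to analyse anyone who took one dose, while a later paragraph leaves dropouts out of the primary analysis without saying that stopping treatment makes a patient a dropout.

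**A reader might infer that old liver disease will be recorded as drug toxicity.** This overlooks attribution, which is assigned to each event and verified by the investigator or physician designee. A dose-limiting toxicity must also be attributable to treatment.

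**Bias is not shown either.** The abnormality predates randomisation and treatment is blinded, so such removals should fall similarly in both arms.

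**Conclusion.** The inconsistency is real, and its reach is limited. The eligibility list contains no liver-function limit, no rule uses the baseline liver tests, and numeric liver limits stand under the Day-15 and Day-29 treatment conditions. On the reading that the heading supports, a patient in the tested subgroup who is above the limits at baseline is dosed for about two weeks (11 to 17 days across the visit window). The patient is then held and, with unchanged values, removed by Day 19 to 25.

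The established consequences are avoidable exposure and truncated treatment. Reduced power is conditional: even if a further 5% to 10% of all randomised patients were lost from the analysis on top of 20% dropout, power at 3.3 points would be 79.6% to 76.8%. The number of patients affected cannot be derived from the documents. The conclusion rests on reading the limits as dosing conditions, which the garbled wording favours but does not settle.

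**What to change.** Reconcile B.7, C.3.2.1, C.3.2.2 and the Day-15/Day-29 instruction with its withholding rule.

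1. State whether the liver limits are dosing conditions or monitoring thresholds, and rewrite the sentence so that it is clear what the closing *if* clause governs.
2. If they are dosing conditions, remove the mismatch in one of two ways. Either make entry consistent with them, using the baseline tests already drawn and for the same subgroup, or express the Day-15/29 condition relative to the baseline value, so that an unchanged pre-existing abnormality is not handled as a toxicity.
3. If they are monitoring thresholds, move them out of the list of conditions and say what follows when one is crossed.

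The choice and the limits are for the sponsor. The cost is a short amendment: one eligibility line or one reworded rule, with no new test. The downside of aligning entry is that a few patients may become ineligible.

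### The Day 15 and open-label dosing condition tolerates a Grade 2 related event, which is looser than the dose-modification table and the open-label entry rules, and nothing says which governs

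*Combined protocol and SAP*

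**What the plan says.** Under Dose Continuation, Modification and Interruption, the instruction for week 3 and open label begins "Prior to initiation of treatment of day 15, and open label phase (Day 29) the patient should have" and lists conditions. A related allergic reaction must have come down to Grade 1 or less. For everything else the requirement is "Any other Panax ginseng-related or identical placebo -related adverse event that may have occurred has resolved to ≤ grade 2 severity". The consequence of failing follows: "If these conditions are not met on Day 15 or Day 29 (all +/- 3 days), the subject will be evaluated weekly". The same sentence fixes when the withholding ends: "Panax ginseng will not be initiated until the toxicity has resolved as described above". A patient may be off drug for one week in total before removal from the treatment phase.

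Next comes a table under the heading "INSTRUCTIONS FOR DOSE MODIFICATIONS OR INTERRUPTION DURING A TREATMENT PHASE", whose action column is labelled Day 2-57. Two of its rows matter most here:

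- "Hypertension, Hypotension, cardiac arrhythmia ≥Grade 2": hold, restart at the 400 mg level once the event is Grade 1 or less. Grade 3 or more means discontinuation.
- Any other non-hematologic toxicity judged related, Grade 2 or more: hold, with the same restart rule.

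Four places limit entry to open label. C.1 and C.6 require the absence of toxicity of Grade 2 or higher, as judged by the PI. C.6.2 and the Toxicity Evaluation paragraph in C.7.2.1 require that the double-blind phase was tolerated without moderate or severe toxicity. The open-label dose is 800 mg per day.

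On labs, C.6.2 lets patients use an outside facility and has the research nurse collect the results. It then says that safety labs on Days 15, 29 and 57 are collected only from patients who come back to the center.

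**The concern.** Day 15 is not the start of a new course. C.6.1 gives twice-daily dosing for 29 days without a break, so on Day 15 the patient is already inside a treatment phase and both texts apply. Day 29 also lies inside the table's range. If the two texts give different answers for the same patient, staff must choose between them. The looser choice continues full dose in a patient whom the table holds, or offers 800 mg per day open label to a patient whom the entry statements exclude. This is a matter of patient safety and uniform conduct. The protocol added its two-phase structure for closer safety monitoring because data in cancer patients were limited, so its dosing rules should give one answer.

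**Working it through.** No sample-size, power or alpha figure bears on this point, so the check is a comparison of the rules by grade. Take a related, non-allergic, non-hematologic event. I read moderate toxicity in C.6.2 as Grade 2, in line with the parallel wording of C.1 and C.6.

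| Status of the event | Week 3/open-label condition | Day 2-57 table | Open-label entry statements |
|---|---|---|---|
| Never above Grade 1 | Met | No hold | Entry allowed |
| Grade 2, ongoing at Day 15 | Met | Hold to Grade 1 or less, then 400 mg level | Not yet relevant |
| Grade 3 earlier, Grade 2 at Day 15 | Met | Still on hold (cardiovascular: discontinued at Grade 3) | Not yet relevant |
| Grade 2, ongoing at Day 29 | Met | Hold | Barred by all four |
| Grade 3 earlier, Grade 2 at Day 29 | Met | Still on hold (cardiovascular: discontinued at Grade 3) | Barred by all four |
| Grade 3, ongoing | Not met | Hold or discontinue | Barred by all four |

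The rules agree at Grade 1 and at Grade 3. They part whenever the current grade is 2.

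- **Threshold.** The difference is 2 − 1 = 1 grade.
- **Dose.** Table A starts at 400 mg twice daily, which is 2 × 400 = 800 mg per day. The reduced level is 400 mg daily. A Grade 2 patient therefore stays at 800 mg per day if the condition alone is followed, and receives nothing if the table is followed. After recovery to Grade 1, the table gives 400 mg per day.
- **Table rows in conflict at Day 15.** Two: the cardiovascular row and the other non-hematologic row.
- **Open-label statements stricter than the condition.** Four: C.1, C.6, C.6.2 and Toxicity Evaluation.

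The conflict has two limits. The allergic condition uses Grade 1 or less in both texts, so there is none there. Hematologic events outside the neutropenia and thrombocytopenia rows are not in the table, so for those the mismatch is only with the open-label entry statements.

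For labs, three texts bear on a remote visit. C.6.2 allows outside draws, and the same section ties Day 15, 29 and 57 safety labs to a return visit. Section III counts missing safety laboratory tests as a major violation, which is a ground for stopping drug and is reportable to the IRB and FDA. The notes to Table 3 allow telephone contact on those days for the symptom and quality-of-life forms. Staff who follow the return-visit sentence could therefore create a reportable violation.

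**The case against.** The best defense is that the condition is only a minimum. It lists what a patient should have before dosing. It does not order dosing, release a hold or undo a discontinuation. The table applies at Day 15 by its own heading, so complying with both texts means following the stricter one. For open label, four consistent statements set the rule, and Section III refers to participants eligible for that phase, which suggests that eligibility is a separate step.

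Much of this stands: a careful reader can reach the safe answer. It does not remove the conflict, because the text goes beyond a minimum. It says drug is withheld "Panax ginseng will not be initiated until the toxicity has resolved as described above", which names a release point. A related Grade 3 nausea that falls to Grade 2 has reached that point, yet the table keeps it on hold. No sentence says the stricter rule prevails. The PI's role in C.1 and C.6 settles who judges toxicity and leaves open which rule applies.

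Some stronger inferences are not supported:

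- A reader might add the discontinuation rows, "Rash, Erythema multiforme ≥ ≥Grade 2" and "Desquamating (blistering) rash- any Grade", and count four conflicting rows. A patient discontinued under those rows is no longer a candidate for Day 15 dosing, and a rash judged to be hypersensitivity falls under the allergic condition. The firm count is two.
- A reader might say that the entry statements never settle whether a resolved event counts. C.6.2 and the Toxicity Evaluation text refer to how the whole double-blind phase was tolerated, so on plain reading a resolved moderate event counts.
- A reader might take the lab sentence as leave to dose untested at-risk patients. Drug is withheld if the listed conditions are not met, and missing safety labs are a major violation. The sentence is contradictory wording and grants no such permission.

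**Conclusion.** The inconsistency is real and should be corrected. The Grade 2 allowance is one grade looser than the table's two hold rows and looser than all four open-label entry statements, and the protocol does not say which governs. The conclusion rests on reading the Day 2-57 label as including Days 15 and 29, and moderate as Grade 2.

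The number of patients affected is unknown, because the documents give no rate of related Grade 2 events or of remote visits. A reader might infer damage to power or to the Day 29 fatigue comparison. Nothing in the documents supports that: no stated design figure depends on this threshold. Scheduled toxicity checks, the one-week limit off drug and investigator-judged discontinuation also limit the harm. The lab contradiction is secondary.

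**What to change.** 1. In the week 3/open-label instruction, change the limit for non-allergic related events from Grade 2 to Grade 1 for events covered by the table's hold rows.
2. Add a sentence stating that the Day 2-57 table, including its discontinuation rows, and the open-label entry rule govern wherever they are stricter.
3. For open label, have the instruction cross-refer to that entry rule.
4. Limit the return-visit sentence in C.6.2 to the optional research blood, so that the outside-facility route already in that section applies to safety labs.

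Items 1 to 3 are wording only. Item 4 may lead to some outside draws, whose number cannot be estimated from the documents, by a route the protocol already provides. Sample size, visit schedule and analysis do not change.
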